## NOTE:

- i. Individual's subject-years at-risk will be calculated for each event type separately and if required for each time period (i.e. for analysis by time period)
- ii. Individual subject-years of follow-up may be required for each time period (i.e. for analysis by time period)

\* Last Contact Date as defined in section 9.5.3

An illustration of follow-up to be counted in each exposure group defined by the two 'Initial Exposure' analysis approaches is shown in Section 9.2.2.

### 9.2.1.2. As-Exposed (Time Varying)

This exposure strategy specifically accounts for treatment switching to or from BENLYSTA throughout the study. It dynamically assigns subjects' exposure group based on Benlysta/non-Benlysta use at time of event, during study follow-up. Therefore, a subject's exposure group can change over time (time varying) depending on the SLE medication in use at specific time during study follow-up. For Benlysta, exposure does not end on the date when Benlysta stops. Instead, two different risk windows will be used to determine when Benlysta exposure ends:

- 14 weeks: Benlysta exposure ends 14 weeks (98 days) after Benlysta treatment stops.
- 6 months: Benlysta exposure ends 6 months (183 days) after Benlysta treatment stops.
- Subjects may contribute events and follow-up time (i.e. subject-years) to either one or both exposure periods depending on the medication switch pattern (see Section 9.2.2). Data summary and analysis will be done by exposure group assigned using the 'As--Exposed' strategy.

In contrast to the 'Initial Exposure' or 'While on Initial Exposure' strategies, which may only utilize subject level exposure group at Enrollment, the 'As-Exposed' strategy (time-varying) will assign and use exposure group at the time of the event.

**Programming Hints for derivation of essential variables needed for computation of incidence and events rates (presented in Section 7.1.5.1) under the 'As-Exposed' approach:**

- Each subject's follow-up time will be split into different exposure periods categorized as 'Exposed' (when the subject is on Benlysta medication) or 'Unexposed' (when the subject is off Benlysta). Each exposure period will have a distinct '*Period Start Date*' and a distinct '*Period end date*'.
  - Note that for each subject, number of exposure periods = number of switches + 1 (see Section 5.1 4 for definition of switching)
- Identify the start of each period as follows:
  - The first exposure period (i.e. period=1) starts from enrollment date (i.e. ***Period Start Date*** = Enrollment Date). First period exposure status is same as baseline exposure group assignment
  - For subsequent exposure periods, ***Periodn+1 Start Date*** is ***Periodn End Date*** + 1
- Identify the end of each period as follows:
  - For all exposure periods except the last, ***Period End Date*** = ***Switch Date***  
***Switch Date*** is  

***Benlysta End Date*** + 98 days or 183 days when switching from Benlysta to Non-Benlysta (i.e. Exposed to Unexposed) period. *Period with this end date will be assigned 'Benlysta' or 'Exposed' group.*

***Next Benlysta Start Date*** – 1 when switching from Non-Benlysta to Benlysta (i.e. Unexposed to Exposed) period. *Period with this end date will be assigned 'Non-Benlysta' or 'Unexposed' cohort*
  - For last or final exposure period, ***Period End Date*** is the ***Last Contact Date***\*

- Identify or map events experienced during the study to the specific exposure period satisfying:

Follow-up Period Start Date ≤ Event Onset Date ≤ Follow-up Period End Date

NOTE: for incidence rate calculation, first event is retained for each exposure group (i.e. Benlysta and Non-Benlysta).

- Calculate individual's subject-years of follow-up for time spent in each exposure group *j* (where *j* =1(Exposed), 2(Unexposed)) as follows:

- For overall or 60-Month+ time period, calculate ‘*period follow-up time*’ (*pFUt*) in days for each period  $i$  ( $i=1, 2, \dots, n$ ) as:
  - (Period End Date – Period Start Date) +1
- For other xx-Month time periods ( $xx = 12, 24, 36, 48$ ), calculate ‘*period follow-up time*’ (*pFUt*) in days as follows:
  - Calculate cumulative follow-up duration for each exposure period  $i$  (CM\_FUD[ $i$ ])
  - Identifying qualifying exposure period for each xx-Month time specific computation as period where previous CM\_FUD value is less than xx-Month target visit day (i.e.  $CM\_FUD[i-1] < xx\text{-Month target visit day}$  for  $i=1, 2, \dots, n$ ; where  $CM\_FUD[0] = 0$ )
  - For each qualifying exposure period for xx-Month time, calculate xx-M\_pFUt =
    - $CM\_FUD[i] - CM\_FUD[i-1]$  if  $CM\_FUD[i] \leq xx\text{-Month target visit day}$
    - $xx\text{-Month target visit day} - CM\_FUD[i-1]$  if  $CM\_FUD[i] > xx\text{-Month target visit day}$
    - where  $CM\_FUD[0] = 0$
- Calculate each individual subject-year of follow-up (*syFUj*) as follows:
  - For each exposure group  $j$  ( $j=1$ (Exposed),  $2$ (Unexposed)), sum *pFUt* over all periods  $i$  with the same exposure group and divided by 365.25
    - $syFU_j = (\sum_{i=1}^n pFU_{t_{i(j)}}) / 365.25$  (for overall or 60+Month time period)
    - $xxM\_syFU_j = (\sum_{i=1}^n xxM\_pFU_{t_{i(j)}}) / 365.25$  (for time period specific computation)

(NOTE: For time period analysis, the above computation will be done for the following time periods: 12-month, 24-month, 36-Month, and 48-Month).

- Individual’s subject-years ‘at-risk’ (*syARj*) will be calculated for each exposure group  $j$  ( $j = 1$ (Exposed),  $2$ (Unexposed)) as follows:
  - Calculate *period ‘at-risk’ time* (*pARTi*) for each exposure period  $i$  ( $i=1, 2, \dots, n$ ) or qualifying exposure period for xx-Month time as:
    - if no event occurred in the exposure period (for overall or 60-Month+ time period calculation) or event day  $> xx\text{-Month target visit day}$  (for xx-Month time period specific calculation)
      - $pART_i = \text{‘period follow-up time’ (pFUt) or}$

$$xxM\_pARt_i = xxM\_pFUt \text{ (for time specific calculation)}$$

- for period where first event occurred (per exposure group) or event day  $\leq$  xx-Month target visit day

$$pARt_i = event\ day - CM\_FUD[i-1]$$

$$xxM\_pARt_i = event\ day - CM\_FUD[i-1] \text{ (in case of time specific calculation)}$$

$$\text{where } CM\_FUD[0] = 0$$

- o For each exposure group  $j$  ( $j=1$ (Exposed),  $2$ (Unexposed)) separately compute individual subject-year at-risk  $syAR_j$  thus:

- For subjects with no events in exposure group  $j$ , sum  $pARt_i$  for all periods  $i(j)$  (i.e. periods occurring while on exposure group  $j$ )

$$syAR_j = (\sum_{i=1}^n pARt_{i(j)})/365.25$$

$$xxM\_syAR_j = (\sum_{i=1}^n xxM\_pARt_{i(j)})/365.25 \text{ (for time period specific computation)}$$

- For subjects with at least one event in exposure group  $j$ , sum  $pARt_i$  for all periods  $i(j)$  up to period where the first event in exposure group  $j$  occurred

$$syAR_j = (\sum_{i=1}^{n^*} pARt_{i(j)})/365.25$$

$$xxM\_syFU_j = (\sum_{i=1}^{n^*} xxM\_pFUt_{i(j)})/365.25 \text{ (for time period specific computation)}$$

where  $n^*$  is the period where the first event was experienced  
(NOTE: Time spent in subsequent exposure periods for the same exposure group after an event had occurred will not be counted)

**NOTE:** Individual's subject-years at-risk will be calculated for each event category separately

\* Last Contact Date as defined in Section 9.5.3

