## 5. CONSIDERATIONS FOR DATA ANALYSES AND DATA HANDLING CONVENTIONS

### 5.1. Study Exposure & Sub-group Display Descriptors

Exposure Group Descriptions			
Study Exposure Group		Data Displays for Reporting	
Code	Description	Description	Order in TLF
A	BENLYSTA	BENLYSTA	2
B	NON-BENLYSTA	NON-BENLYSTA	1

Exposure group comparisons will be displayed using the following specified descriptors:

- BENLYSTA vs NON-BENLYSTA

BENLYSTA group is used for subjects who are exposed to Benlysta while NON-BENLYSTA group is used for subjects who are not exposed to Benlysta. For summary description of baseline characteristics, the exposure group represents subjects' exposure at enrollment (i.e 'Initial Exposure'). For summary of safety and effectiveness endpoints, the exposure group will be defined using the 'Initial Exposure', 'As-Exposed', and/or 'Ever-Exposed' strategies (see Appendix 2, Section 9.2). 'As-Exposed' is defined based on whether or not a subject is using Benlysta at specific period during the study follow-up time; thus a subject's exposure group can change over time depending on switching to or off Benlysta. 'Ever-Exposed' is defined based on whether a subject was exposed to Benlysta at any point in time after enrollment, in this instance a subject's exposure can change only once over time if they were initially 'Unexposed' and then started using Benlysta; once a subject is exposed to Benlysta, they will always be considered as 'Exposed'.

The specific strategy for defining exposure group and the analysis approach for accrued data will be indicated on the TLFs titles and list of the planned data displays provided in Appendix 11 (Section 9.11).

---

 Subjects are considered to have switched from BENLYSTA exposure group if they permanently discontinued Benlysta treatment or missed doses of Benlysta for more than 98 days and do not restart doses of Benlysta on or before day 99 after the last Benlysta medication end date. Subjects are considered to have switched from NON-BENLYSTA exposure group if they initiate or start receiving Benlysta dose anytime during the study follow-up period. Change of different study-qualifying Non-Benlysta Standard of Care (SOC) medications does not count as exposure switching.

Primary analysis will be done on ‘Initial Exposure’ strategy for all endpoints while ‘As--Exposed’ and ‘Ever-Exposed’ will apply for some endpoints as exploratory analysis:

Endpoints	Primary analysis		Exploratory analysis	

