
1. Incidence rate will be calculated for each exposure group as follows:
 $\text{Incidence Rate} = \frac{\sum \text{at risk subjects with at least one event}}{\sum \text{subject years at risk}} \times 100$ 
 
- Incidence rate is defined as the number of 'at-risk' subjects experiencing first event (i.e. number of new cases) during the specified follow-up period divided by total subject-years at-risk of that event for all subjects at risk.
 
- Although the categorization of study follow-up time to Benlysta (Exposed) or Non-Benlysta (Unexposed) depends on the exposure assignment strategy (see Appendix 2, Section 9.2.1 for further discussion), the follow-up time included in the subject-years at-risk calculation, for each month xx time period, starts from enrollment date and ends at the earliest of the following: 
 
o First event date
 
o Last contact date (as defined in Section 9.5.3)
 
o Month xx target date (Section 5.3)
 
o Censored date (for While on Initial Exposure strategy; see Section 9.2.1.1)
 
o Data cut-off date
 
 
Additionally, for some exposure strategies (e.g. 'As-Exposed' strategy; see Appendix 2, Section 9.2.1.2), time to treatment switch and risk windows are also considered when categorizing follow-up time into 'Exposed' and 'Unexposed' period.
 
 
- Calculation of an individual's subject-years at-risk for each exposure strategy is shown in Section 9.2.
 
- Subject-years at-risk will be calculated for each event type separately.
 
- Only the first experience of the event (i.e. new cases) or first primary diagnosis (in the case of a malignant event) which occurred during the 'at-risk' period are counted (see Section 9.2.1 for time period considered for each exposure strategy).
 
- For summary of each specific AESI category, subjects experiencing events in multiple AESI categories will be counted in more than 1 AESI category.
 
 
2. Event rate will be computed for each exposure group as follows:
 $\text{Event rate} = \frac{\sum \text{all AESI events}}{\sum \text{subject years of follow-up}} \times 100$ 
 
- Event rate is estimated for potentially recurrent events and represents the average number of events per unit time of follow-up. It is defined as the total number of events experienced by all subjects during the specified study period divided by subject-years of follow-up. The categorization of study follow-up time depends on the exposure strategy (see Appendix 2, Section 9.2.1). The subject-years of follow-up for each month xx time period takes the same definition above for the subject-years at-risk, however, follow-up does not stop at the time of first event.
 
- Additionally, for some exposure strategies (e.g. 'As-Exposed' strategy), time to treatment switch and risk windows are also considered when categorizing follow-up time into exposed and unexposed period (Section 9.2.1.2)
 
- All events experienced during the follow-up period including recurrent events are counted (see Section 9.2.1 for time period considered for each exposure strategy).
 

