### 9.2.2. Exposure Strategy Hypothetical Illustration

The exposure status strategies described in Section 9.2.1 are illustrated in the chart below showing treatment profile of six hypothetical subjects.

[figure not shown]
NOTE: The risk windows are only applicable when switching from Benlysta medication to Non-Benlysta Standard of Care (SOC) medication(s). There are two possible risk windows: (1) 14 weeks (98 days) which assumes that Benlysta exposure ends 14 weeks (98 days) after cessation (End Date) of Benlysta medication; and (2) 6 months.

The events and exposure time contributed by each subject to the two exposure status cohorts (Benlysta or Non-Benlysta) depend on the analysis strategy as shown in the Table below.

Exposure Strategy	Highlights	Exposure Time/Events Attribution per risk windows*	
		BENLYSTA	NON-BENLYSTA

Initial Exposure:
 
 
- Intent-To-Treat (ITT)
 
- While On-Initial Exposure
 
	
ITT
 
 
• Assign exposure status based on baseline (enrollment) SLE medication
 
• Include all events and exposure time during FU irrespective of switching
 
 
While On-Initial Exposure
 
 
• Assign exposure status based on baseline (enrollment) SLE medication
 
• Censor (exclude) events and exposure time post switching
 
	
D – A (subjects 1, 3, 6)
 
D – A (subject 1) B2 – A (subjects 3 & 6)
	
d – a (subjects 2, 4, 5)
 
d – a (subject 2) b - a (subjects 4 & 5)

As-Exposed (Time varying)
	
 
• Allows subjects to switch treatment exposure status based on treatment use
 
• Assign time varying treatment exposure group
 
• Subjects treatment exposure group change over follow-up time depending on switch on and off Benlysta medication
 
• Treatment exposure status is assigned at event and visit data level
 
• Used all data since no censoring of events or follow-up exposure time after switching
 
• Subjects can contribute person-year exposure time to any of treatment exposure groups
 
	
D – A (subject 1) B2 – A & D – C (subject 3) c2 – b (subject 4) d - b (subject 5) B2 – A (subject 6)
	
d – a (subject 2) C – B2 (subject 3) b – a & d – c2 (subject 4) b – a (subject 5) D – B2 (subject 6)

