Disposition Duration 
 
Duration since last known visit or last contact date                             
 
Subject who has an 'Ongoing' status on the database (applicable to final analysis dry-run) will be categorized by duration since last contact calculated as: (DataCut Off Date (DCO) – Last Contact Date +1)/365.25
 
The following categories will be used:                                     
 
Last contact date to DCO is < 0.5 year
 
 
 
 
 

 
- Last contact date to DCO is 0.5 - < 1 year
 
- Last contact date to DCO is 1 - < 2 years
 
- Last contact date to DCO is 2 - < 3 years
 
- Last contact date to DCO is 3 - < 4 years
 
- Last contact date to DCO is 4+ years
 

 
• Last contact date definition:             
 
○ maximum (death date [supersedes all other dates], last data assessment date, last visit date, last AE or hospitalization date)
 
○ in the case that the above date is greater than the reference end date (date of completion or withdrawal from end of study disposition CRF page), then the last contact date will be replaced with the reference end date. This is equivalent to the risk end period for each subject, and will be used for the subject-years calculations.
 
 
 

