24.122	Evaluable	Overall Proportion and Rates of Adverse Events of Special Interest [While On Initial Exposure Strategy] – Treatment Initiators	
24.210	Evaluable	Rates of Adverse Events of Special Interest by Time Period [As-Exposed – Time Varying Strategy with 14 Weeks Risk Window]	
24.211	Evaluable	Rates of Adverse Events of Special Interest by Time Period [As-Exposed – Time Varying Strategy with 14 Weeks Risk Window] – Current Users	
24.212	Evaluable	Rates of Adverse Events of Special Interest by Time Period [As-Exposed – Time Varying Strategy with 14 Weeks Risk Window] – Treatment Initiators	
24.310	Evaluable	Rates of Mortality, Serious Infections, Opportunistic Infections, Other Infections of Interest and Serious Psychiatric Events by Time Period [As-Exposed - Time Varying Strategy with 6 Months Risk Window]	
24.311	Evaluable	Rates of Mortality, Serious Infections, Opportunistic Infections, Other Infections of Interest and Serious Psychiatric Events by Time Period [As-Exposed – Time Varying Strategy with 6 Months Risk Window] – Current Users	

Safety Endpoints Tables			
Table No	Analysis Population	Title	Programming Note
24.312	Evaluable	Rates of Mortality, Serious Infections, Opportunistic Infections, Other Infections of Interest and Serious Psychiatric Events by Time Period [As-Exposed – Time Varying Strategy with 6 Months Risk Window] – Treatment Initiators	
24.410	Evaluable	Rates of Mortality, NMSC and Malignancies by Time Period [Ever-Exposed Strategy]	
24.411	Evaluable	Rates of Mortality, NMSC and Malignancies by Time Period [Ever-Exposed Strategy] – Current Users	
24.412	Evaluable	Rates of mortality, NMSC and Malignancies by Time Period [Ever-Exposed Strategy] – Treatment Initiators	

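### The 6-month As-Exposed derivation counts switches with a 98-day rule but ends exposure at 183 days, so some restarts produce negative unexposed time

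*SAP*

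**What the plan says.** SAP 5.1 (footnote 1) has one definition of leaving the Benlysta group: permanent discontinuation, or more than 98 days of missed doses in patients who "do not restart doses of Benlysta on or before day 99 after the last Benlysta medication end date". A restart on day 100 or later therefore follows a switch.

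SAP 9.2.1.2 sets two risk windows, 98 and 183 days. For the longer one, "Benlysta exposure ends 6 months (183 days) after Benlysta treatment stops". The programming hints state that "number of exposure periods = number of switches + 1" and point to Section 5.1 for what a switch is, without distinguishing the windows. The dates then follow these rules:

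- An exposed period that is not the last ends at the Benlysta end date plus "98 days or 183 days when switching from Benlysta to Non-Benlysta (i.e. Exposed to Unexposed) period".
- Each later period starts the day after the previous one ends.
- An unexposed period that is not the last ends the day before the next Benlysta start.
- The last period ends at Last Contact Date.
- Length is end minus start plus one, with no floor at zero.

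Two other sections govern where follow-up stops. In SAP 7.1.5.1 the time at risk "starts from enrollment date and ends at the earliest of the following", and the list includes last contact. SAP 9.5.3 says of the last contact date: "This is equivalent to the risk end period for each subject, and will be used for the subject-years calculations".

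The 6-month window feeds Tables 24.310 to 24.312, titled "Rates of Mortality, Serious Infections, Opportunistic Infections, Other Infections of Interest and Serious Psychiatric Events by Time Period". SAP 5.1 labels As-Exposed exploratory. Protocol 8.3.2 names the 6-month window among the planned analyses of infections and mortality.

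For Ever-Exposed, SAP 9.2.1.3 keeps the first event in each exposure group, and SAP 9.2.2 does so for hypothetical subjects 4 and 5. The at-risk formula in 9.2.1.3 sets Benlysta time to zero if the event came before Benlysta started. SAP 7.1.5.1 ends at-risk time at the first event and counts only the first primary malignancy.

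**The concern.** The rule that opens an unexposed period and the window that closes an exposed one have to be the same length. In the 14-week analysis they are. In the 6-month analysis the switch is triggered at about 98 days and exposure runs to 183, so a patient who restarts in between is given an unexposed period that ends before it begins. The days come out of the Non-Benlysta denominator and are added to the Benlysta one. The two exposed periods also overlap, so an event between the restart and the end of the window maps to both.

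The last-contact case has a related cause. Nothing in 9.2.1.2 stops an exposed period from running past the end of follow-up. While On Initial Exposure (9.2.1.1) does take the minimum of switch date and last contact; As-Exposed does not.

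At stake are the person-year denominators of the As-Exposed rates and, for Ever-Exposed, whether a numerator can be counted without its denominator.

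**Working it through.** **Window lengths.** 14 × 7 = 98 days. By the target-day rule in SAP 5.3, 365.25/12 × 6 = 182.625, rounded up to 183. Both match the SAP.

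**Restart inside the 6-month window.** Let E be the stop day, E + r the restart day and W the window.

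1. Exposed period 1 ends on E + W.
2. The unexposed period runs from E + W + 1 to E + r − 1.
3. Its length is (E + r − 1) − (E + W + 1) + 1 = r − (W + 1).
4. A switch is recognised only for r ≥ 100 (SAP 5.1).

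With W = 98 the length is r − 99, which is +1 at r = 100 and never negative. With W = 183 it is r − 184:

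| Gap r (days) | Unexposed days | Exposed days (follow-up to day 1827) |
|---|---|---|
| 100 | −84 | 1,911 |
| 120 | −64 | 1,891 |
| 150 | −34 | 1,861 |
| 183 | −1 | 1,828 |
| 184 | 0 | 1,827 |

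The fault covers exactly r = 100 to 183. Exposed and unexposed days still sum to 1,827 overall, but they are misallocated.

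**By time period.** Stop day 200, restart day 320, last contact day 1827. The periods end on days 383, 319 and 1827, so cumulative follow-up is 383, 319, 1827.

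- 12 months (target day 366): period 1 gives 366. Period 2 does not qualify, because 383 is not below 366. Period 3 qualifies, because 319 is below 366, and gives 366 − 319 = 47. Total: 366 + 47 = 413 exposed days in a 366-day period.
- 24 months (target day 731): exposed 383 + (731 − 319) = 795; unexposed 319 − 383 = −64.
- First event on day 1000: Benlysta at-risk time is 383 + (1000 − 319) = 1,064 days, although only 1,000 days have passed.

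**Last contact inside the window.** A permanent stop on day E with last contact on E + d gives a last period from E + W + 1 to E + d, of length d − W. For W = 98 and d = 50 this is −48 days. For W = 183 and d = 150 it is −33 days.

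**Scale (assumption: gaps spread evenly over 100 to 183 days).** The mean of 184 − r is 42.5 days, or 42.5/365.25 = 0.116 person-years per restart. The documents give no count, so as a range, 20 to 400 such restarts (1% to 20% of the planned 2,000 Benlysta patients) move 2.3 to 46.5 person-years. That is 0.06% to 1.20% of the planned 3,886 comparison person-years. The 3,886 ignores crossover, so it is only a yardstick for the As-Exposed denominator.

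**Ever-Exposed.** Enrolment day 1, event day 200, Benlysta start day 400, second event day 700. The per-group event rule counts the day-700 event for Benlysta, while the zero branch gives no Benlysta time: one event over 0 person-years. Time kept per group would be (700 − 400 + 1)/365.25 = 0.824 person-years. With no second event and last contact on day 1827, the two rules give 0 and (1827 − 400 + 1)/365.25 = 3.910. If 10% to 50% of 1,000 comparators start Benlysta after 1 to 2.5 years (assumed), then at the protocol's 0.226 per 100 patient-years the subjects with an earlier event number between 1,000 × 0.1 × 1 × 0.00226 = 0.2 and 1,000 × 0.5 × 2.5 × 0.00226 = 2.8 per malignancy category.

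**The case against.** The best reply is that this is a gap in programming hints and not a wrong analysis. The descriptive text of 9.2.1.2 and protocol 8.3.2 are clear that 6-month exposure lasts until 183 days after stopping, so a shorter gap holds no comparison time. A period that ends before it starts would be noticed. The analysis is exploratory and the effect looks negligible.

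The intent is indeed clear, and the weight is limited. But 7.1.5.1 sends the reader to 9.2 for the subject-years calculation, so the hints are the operative definition, and the obvious repairs differ. For a 120-day gap, setting the negative period to zero leaves 1,891 exposed days in 1,827 days of follow-up; joining the two exposed periods gives 1,827. The SAP should choose.

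For the last-contact case, one can argue that no switch has occurred until the 98 days have run out. That reading removes the −48-day example. It does not remove the 183-day one: last contact 150 days after stopping is past the switch threshold and still inside the window.

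On Ever-Exposed, the zero branch is coherent with 7.1.5.1, since a patient with an earlier malignancy is no longer at risk of a first one. If the branch is instead read exposure period by exposure period, it has no case to apply to. Either reading leaves a conflict with another part of the text, so this objection changes the remedy and not the need for one.

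**Conclusion.** The derivation in SAP 9.2.1.2 is wrong as written for the 6-month window, and it lacks a cap at last contact for both windows. The restart fault affects Tables 24.310 to 24.312. The last-contact fault also reaches the 14-week As-Exposed tables. The arithmetic is exact. The effect on reported rates cannot be computed without gap frequencies and is probably small; the scale figures rest on assumed counts, evenly spread gaps and a denominator that ignores crossover.

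A reader might infer more than the documents support:

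- That the primary analyses are affected. ITT uses no switch. While On Initial Exposure uses only the 98-day window, caps at last contact, refers to Section 5.1 for switching and keeps the whole study period if there is none, so its reference to the baseline medication's end date does not by itself censor patients who stay on Benlysta.
- That the one-day difference between the restart limits in SAP 5.1 and 9.5.2 changes censoring. The 9.5.2 limit classifies Benlysta as historical or baseline around enrolment; it is not the follow-up switching rule.
- That Benlysta at-risk time in Ever-Exposed should simply restart at Benlysta start. 7.1.5.1, the per-group event rule and the zero branch point in different directions, and the documents do not say which governs.

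This is a specification defect that should be fixed before the final tables are run. It is not evidence of a materially wrong rate.

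**What to change.** In SAP 9.2.1.2:

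- Define the switch off Benlysta with the same window W (98 or 183 days) that ends exposure, so that a restart within the window continues the exposed period. Count switches and periods separately for each window. A gap of exactly W + 1 days gives zero unexposed days, so the boundary day does not matter here. The 98-day definition in 5.1 can stay for While On Initial Exposure.
- Set the end of an exposed period to min(Benlysta episode end + W, Last Contact Date), and create no unexposed period when Last Contact Date comes first. This matches 7.1.5.1 and 9.5.3.
- Add a program check that no period has negative length and that the periods of each subject sum to follow-up.

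In SAP 9.2.1.3, reconcile the per-group event rule (and subjects 4 and 5 in 9.2.2), the zero branch and 7.1.5.1, so that an event counts for Benlysta only if the matching at-risk time is counted too. Whichever rule is chosen should be stated.

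The cost is a few lines of SAP text and a derivation update, with no new data. Restarts 100 to 183 days after stopping become continuous exposure in the 6-month analysis, which the window definition already implies.

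### SAP 9.2.1.2: the As-Exposed formulas do not limit a non-final BENLYSTA period at last contact, contradict SAP 7.1.5.1 and 9.5.3, and can yield negative NON-BENLYSTA time if coded literally

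*SAP*

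**What the plan says.** SAP 9.2.1.2 (As-Exposed, Programming Hints) splits each patient's follow-up into exposed and unexposed periods under these rules:

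- The count of periods is fixed: "number of exposure periods = number of switches + 1".
- Every period except the last ends at the Switch Date. For a move off BENLYSTA, this is the BENLYSTA end date plus "98 days or 183 days when switching from Benlysta to Non-Benlysta (i.e. Exposed to Unexposed) period".
- Only the last period ends at Last Contact Date.
- Each later period starts the day after the previous one ends.
- Period length is end minus start plus 1, with no floor at zero.

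The switch definition is in the footnote to SAP 5.1. A patient has left the BENLYSTA group "if they permanently discontinued Benlysta treatment or missed doses of Benlysta for more than 98 days" without a restart by day 99. Nothing there requires follow-up to reach the end of the risk window.

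The general rule is in SAP 7.1.5.1. Counted time "starts from enrollment date and ends at the earliest of the following" dates, one of which is "Last contact date (as defined in Section 9.5.3"). Event-rate follow-up has the same definition, except that it does not stop at the first event. SAP 9.5.3 treats last contact as the end of each patient's risk period for the subject-years calculations.

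**The concern.** A patient who stops BENLYSTA for good has one switch, hence two periods, and the BENLYSTA period is not the last. If that patient's last contact comes before stop + 98 (or + 183) days, the BENLYSTA period ends after the patient was last observed. The second period then ends before it starts.

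The formulas for the other strategies do not have this gap. ITT and Ever-Exposed run to last contact. While On Initial Exposure takes an explicit minimum of First Switch Date and Last Contact Date.

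At stake is the person-time denominator of the As-Exposed displays (Tables 24.210 to 24.212, 24.310 to 24.312 and 13.310). In the overall calculation, BENLYSTA rates would be a little too low and NON-BENLYSTA rates a little too high. The patients affected are those who stop shortly before they leave, die or complete follow-up.

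**Working it through.** **Base figures.** The SAP gives no numerical example for these formulas. The planned patient-years can be reproduced from constant 10% annual drop-out over 5 years (protocol 8.2): N x (1 - 0.9^5)/(-ln 0.9). This gives 7,773.5 for N = 2,000 and 3,886.8 for N = 1,000, against the stated 7,773 and 3,886.

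**One patient, formulas taken literally.** Stop on day 330, last contact on day 340, 98-day window.

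- BENLYSTA period: day 1 to 330 + 98 = 428, so 428 days.
- NON-BENLYSTA period: day 429 to day 340, so 340 - 429 + 1 = -88 days.
- Correct values: 340 and 0.
- The sum is 428 - 88 = 340, so a check on total follow-up would not reveal the error.

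**12-month table, same patient.** The target day is 366. Cumulative follow-up after period 1 is 428, above 366, so period 1 is cut to 366 days. Period 2 qualifies only if 428 < 366, so it drops out. The table counts 366 days instead of 340: 26 days after last contact, with no offset.

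**Other cases, overall calculation.**

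| Stop / last contact (day) | Window (days) | Literal BENLYSTA / NON-BENLYSTA | Capped |
|---|---|---|---|
| 700 / 730 | 98 | 798 / -68 | 730 / 0 |
| 700 / 730 | 183 | 883 / -153 | 730 / 0 |
| 1000 / 1120 | 98 | 1098 / 22 | 1098 / 22 |
| 1000 / 1120 | 183 | 1183 / -63 | 1120 / 0 |

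**Mortality incidence.** Take a stop on day 700, death on day 730 and the 98-day window. At-risk time in the event period is event day minus prior cumulative time, 730 - 0 = 730, which is correct. NON-BENLYSTA has no event, so it takes the full second period, 730 - 798 = -68. Only the negative half arises.

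**Size if stopping and leaving are independent.** The stopping hazard s is not in the documents; 0.1 to 0.2 per year is assumed. Let d = -ln 0.9 = 0.1054, and let w be the window in years (98/365.25 = 0.268 or 183/365.25 = 0.501). Write k = s + d. For 2,000 patients:

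- Stops during follow-up: 2000 x (s/k) x (1 - e^(-5k)).
- Stops per year near Month 60: 2000 x s x e^(-5k).
- Misplaced person-years: about (stops x d + stops per year near Month 60) x w^2/2.

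Low end (s = 0.1, 98 days): (625 x 0.1054 + 71.6) x 0.0360 = 4.9. High end (s = 0.2, 183 days): (1,025 x 0.1054 + 86.9) x 0.1255 = 24.4 to 24.5.

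A simulation gives the same 4.9 and 24.4, with 2 to 5% of patients affected. It also gives the correct denominators: BENLYSTA 6,413 (low) and 5,614 (high); NON-BENLYSTA, which is 3,886 plus true off-drug time, 5,246 and 6,045. The shifts are:

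- Low: 4.9/6,413 = +0.08% BENLYSTA; 4.9/5,246 = -0.09% NON-BENLYSTA.
- High: 24.4/5,614 = +0.43%; 24.4/6,045 = -0.40%.
- At the high end the crude rate ratio is multiplied by (1 - 0.0040)/(1 + 0.0043) = 0.992.

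**Size if leavers tend to stop just before leaving.** Early leavers number 2,000 x (1 - 0.9^5) = 819. Assume that 10 to 50% of them stop within the window before leaving, with a uniform gap. The misplaced time is 819 x share x w/2, set here against 7,773 and 3,886:

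- 98 days: 11 to 55 person-years, BENLYSTA +0.1 to +0.7%, NON-BENLYSTA -0.3 to -1.4%.
- 183 days: 21 to 103 person-years, +0.3 to +1.3%, -0.5 to -2.6%. At the top the rate ratio factor is (1 - 0.0264)/(1 + 0.0132) = 0.961.

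**The case against.** The strongest reply is that the SAP already holds the limit. Section 7.1.5.1 is the parent rule for these hints and ends counted time at last contact. It uses switch dates and risk windows only to divide follow-up, not to extend it. Section 9.5.3 says the same of last contact. Section 9.2.1.2 can also be read so that, when the window outlasts follow-up, the patient never becomes unexposed; BENLYSTA is then the last period and ends at last contact. On that reading nothing goes wrong.

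Much of this stands. A reader might infer that the SAP has no limit at last contact anywhere and that BENLYSTA rates are bound to be biased down. The documents do not support that. A reader might also infer that patients who die inflate the BENLYSTA denominator of the mortality rate. They do not; for them, excess BENLYSTA time can arise only for other AESI that they did not have and in event-rate follow-up.

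The reply does not remove the contradiction. Section 7.1.5.1 sends the individual calculation to Section 9.2, where the programmer meets the uncapped formula. Treating BENLYSTA as the last period departs from the fixed count of switches plus 1 under the Section 5.1 definition. Routine checks might catch negative records, but the 12-month case produces none and the overall total reconciles.

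It is also fair that the effect is small. Protocol Table 8-1 plans a half-width of 0.93 on 5.80 for serious infection (16%) and 0.32 on 0.68 for deaths (47%).

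**Conclusion.** The point holds as a formula that contradicts the SAP's own general rule. Read with the switch definition, Section 9.2.1.2 can produce person-time after last contact and negative person-time, and neither is valid.

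The consequence is limited. As-Exposed is labelled exploratory in SAP 5.1. The primary ITT and While On Initial Exposure results, and the weighted analyses built on them, are untouched. No hypothesis is tested.

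If the formulas are coded literally, the overall As-Exposed rates move slightly in favour of BENLYSTA. The shift is about 0.1 to 0.4% of each denominator under independence, given an assumed stopping hazard of 0.1 to 0.2 per year. Shifts of up to a few percent need a large share of leavers to stop just before leaving. The documents give no such share, and protocol 6.2 and 6.4 say that patients are followed regardless of changes in medication.

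**What to change.** In SAP 9.2.1.2:

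- Set Period End Date = min(Switch Date, Last Contact Date) for every period.
- Create a later period only if it starts on or before Last Contact Date, and count periods accordingly.
- Apply both rules before computing CM_FUD, so that the 12- to 48-month tables are also correct.

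Section 9.2.1.2 then agrees with 7.1.5.1, 9.5.3 and the While On Initial Exposure formula. A check that no period has negative length, and that none ends after last contact, would confirm the code. The cost is a line or two of SAP text and programming; no new data are needed.

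One neighbouring case is not cured by this cap. The switch definition uses 98 days even when the window is 183. A restart on day 640 after a stop on day 500 therefore gives an unexposed period from day 684 to day 639, or -44 days. The switch definition should be aligned with the window in use in the same edit.
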